2. SYNOPSIS

Name of Sponsor/Company: Alkermes, Inc.

Name of Investigational Product: ALKS 3831

Name of Active Ingredient: Olanzapine and samidorphan

Title of Study: A Phase 3, Multicenter Study to Assess the Long Term Safety and Tolerability of ALKS 3831 in Subjects with Schizophrenia

Investigators: This is a multinational, multicenter study.

Study Period:	Phase of Development: 3
Estimated date of first subject's consent: Q1 2016	
Estimated date of last subject's last visit: Q4 2018	

Objectives:

Primary: The primary objective of this study is to evaluate the long-term safety and tolerability of ALKS 3831 in subjects with schizophrenia.

Methodology: Subjects that have completed the 4-week Treatment Period of the antecedent study, ALK3831-A305, within the past 7 days are eligible to be enrolled in this study. Subjects completing the antecedent study as inpatients may continue as inpatients for up to 1 week in this extension study. These subjects may be discharged from the inpatient unit at any time during this week based on Investigator's judgment.

[figure not shown]
Subjects enrolled in the study will be started on ALKS 3831 10/10 (10 mg olanzapine/10 mg samidorphan). The dose may be increased to ALKS 3831 15/10 (15 mg olanzapine/10 mg samidorphan) and up to ALKS 3831 20/10 (20 mg olanzapine/10 mg samidorphan) during the first week or thereafter, based on Investigator discretion. For subjects entering this study as outpatients, study staff will check in with them by phone on Day 3 to assess tolerability and determine if a dose increase is needed. An Unscheduled Visit will be arranged mid-Week 1 for subjects requiring a dose increase to ALKS 3831 15/10 or ALKS 3831 20/10. Following a dose increase, the dose may be decreased back to 10/10 or 15/10 if there are tolerability issues. Thus, dosing is flexible and subjects will receive ALKS 3831 10/10, 15/10, or 20/10 throughout the duration of the study, based on Investigator discretion. Dose adjustments can only be performed on-site at the study center. Subjects requiring dose adjustments between visits should arrange an Unscheduled Visit where the following procedures will be performed: study drug return, adherence review, and study drug dispensation.

Safety assessments will include adverse event (AE) monitoring, clinical laboratory testing, vital signs, weight and waist circumference assessments, 12-lead electrocardiograms (ECGs), movement disorder assessments, including the Abnormal Involuntary Movement Scale (AIMS), Barnes Akathisia Rating Scale (BARS), and Simpson Angus Scale (SAS), and the Columbia-Suicide Severity Rating Scale (C-SSRS).

Antipsychotic efficacy assessments to evaluate durability of treatment effect include Positive and Negative Syndrome Scale (PANSS) and Clinical Global Impressions-Severity (CGI-S).

Additional assessments include the Impact of Weight on Quality of Life–Lite Questionnaire (IWQOL-Lite), Cigarette Use, and EuroQOL-5D (EQ-5D).

Subjects completing 52 weeks of treatment with study drug will be eligible to continue in the open-label, long-term safety study (ALK3831-A308) and will continue to receive ALKS 3831. Subjects not continuing in the ALK3831-A308 long-term safety study will enter a 4-week Safety Follow-up Period. A schematic summarizing the study design is shown below.

Criteria for Evaluation:

Safety:

The safety assessments include:

- Adverse events (AEs)
- Clinical laboratory parameters (chemistry, hematology, and urinalysis)
- Vital signs (oral temperature, respiratory rate, orthostatic blood pressure, and pulse)
- Weight and waist circumference
- ECG parameters (heart rate, RR, PR, QRS, and QT)
- C-SSRS
- AIMS
- BARS
- SAS

Efficacy:

The efficacy assessments include:

- PANSS
- CGI-S

Other:

Other assessments include:

- IWQOL-Lite
- Cigarette Use
- EQ-5D

Statistical Methods:

The Safety Population is defined as all enrolled subjects who receive at least one dose of ALKS 3831 in this study. The Full Analysis Set (FAS) Population is defined as all subjects that receive at least one dose of ALKS 3831 and at least one postdose PANSS assessment in this study.

Safety analyses will be carried out using the Safety Population. Incidence of AEs will be analyzed as a safety endpoint. Reported AE terms will be coded using the Medical Dictionary for Regulatory Activities (MedDRA[®]) and will be summarized by system organ class and preferred term categories. Serious AEs and AEs leading to study discontinuation (AEDCs) will also be summarized.

Observed values and changes from Baseline in weight, body mass index (BMI), waist circumference, laboratory parameters, vital signs, and ECG parameters will be summarized by study visit. Prior and concomitant medication use will be summarized by World Health Organization (WHO) Drug Dictionary Anatomical Therapeutic Class (ATC) code.

Efficacy analyses will be carried out using the FAS Population. The following efficacy endpoints will be analyzed to evaluate the durability of treatment effect for ALKS 3831:

- Change from Baseline in PANSS total score and subscales by visit
- Change from Baseline in CGI-S by visit
- PANSS response
- Relapse
- Remission

• Time to discontinuation

The PANSS (total and subscale scores) and CGI-S scores, and appropriate changes from Baseline, will be summarized using descriptive statistics. Positive and Negative Syndrome Scale response and remission at each visit will be summarized as number and percentage.

The discontinuation rate and the relapse rate will be estimated using the Kaplan-Meier (KM) Method and the KM plot will be provided.

Sample Size Considerations: Approximately 390 subjects are planned to be enrolled in this study.

4. LIST OF ABBREVIATIONS

The following abbreviations are used in this study protocol.

I able 2: List of Abbreviations and Definitions of Term	Fable 2:	List of Abbreviations and Definitions of Terms
---	----------	--

Abbreviation or Term	Explanation or Definition
AE	Adverse event
AIMS	Abnormal Involuntary Movement Scale
ATC	Anatomical Therapeutic Chemical [classification system]
BARS	Barnes Akathisia Rating Scale
BMI	Body mass index
CGI-S	Clinical Global Impression-Severity
CRO	Contract research organization
CSA	Clinical Study Agreement
C-SSRS	Columbia-Suicide Severity Rating Scale
EC	Ethics Committee
ECG	Electrocardiogram
eCRF	Eectronic case report form
EOT	End of treatment
EQ-5D	EuroQOL-5D
ET	Early termination
FAS	Full analysis set
GCP	Good Clinical Practice
HbA1C	Hemoglobin A1c
ICF	Informed consent form
ICH	International Conference on Harmonisation of Technical Requirements for Registration of Pharmaceuticals for Human Use
IWQOL	Impact of Weight on Quality of Life
IRB	Institutional Review Board
КМ	Kaplan-Meier
MedDRA	Medical Dictionary for Regulatory Activities
PANSS	Positive and Negative Syndrome Scale
РСР	Phencyclidine
PI	Principal Investigator
SAE	Serious adverse event
SAS	Simpson-Angus Scale

Table 2. List of	Abbreviations and Definitions of Terms (Continued)
Abbreviation or Term	Explanation or Definition
WHO	World Health Organization

Table 2: List of Abbreviations and Definitions of Terms (Continued)

5. INTRODUCTION

5.1. Background

Schizophrenia is a chronic, severe disease with debilitating psychotic symptoms, physical and psychiatric comorbidities, and increased mortality. Despite the availability of a range of FDA-approved medicines, the disease is still inadequately treated, and is associated with enormous human and economic cost. Life expectancy is reduced by 19 years in men and 16 years in women with schizophrenia compared to the general population (Harris and Barraclough 1998; Lambert et al, 2010; Tiihonen et al, 2009). The decreased life expectancy is due to a combination of direct effects of the disease, eg, increased rates of suicide and violence (Hodgins 2008; Kuo et al, 2005), as well as indirect causes, including increased incidence of obesity and cardiovascular disease (Nasrallah et al, 2006; Saha et al, 2007).

The goal of treatment in schizophrenia is to achieve the maximal reduction in positive and negative symptoms and increase functionality. Unfortunately, even with regular administration of currently available antipsychotic medications at full therapeutic dose levels, the overwhelming majority of patients continue to exhibit residual active symptomatology. For physicians and patients, in many cases the current treatment paradigm involves an efficacy/tolerability trade-off, where use of the most efficacious agents is avoided or delayed in order to avoid known safety issues. As such, there is a need for more efficacious therapies with better tolerability.

Olanzapine is regarded as one of the most effective antipsychotic agents with well-recognized efficacy and decreased incidence of extrapyramidal symptoms. However, its efficacy is compromised by safety and tolerability limitations that affect compliance and retention of patients on olanzapine therapy (Lieberman et al, 2005). In particular, results of the Clinical Antipsychotic Trials of Intervention Effectiveness (CATIE), identify olanzapine as an effective atypical antipsychotic associated with the highest weight gain (9.4 kg increase over a treatment period up to 18 months and \geq 7% body weight in 30% of subjects) and a comparatively higher discontinuation rate relative to other antipsychotic agents due to weight gain and metabolic effects. As a result of these limitations surrounding safety, tolerability, adherence, and retention, the risk of olanzapine therapy can outweigh the benefit, and patients are often switched to alternative antipsychotic agents even if they are less effective.

ALKS 3831 is a fixed-dose combination product of olanzapine and samidorphan (a μ -opioid antagonist) under investigation for the treatment of schizophrenia. Phase 1 and Phase 2 studies demonstrated that coadministration of samidorphan with olanzapine attenuates the weight gain experienced with olanzapine alone. Results from these studies are described in more detail in Section 5.3. ALKS 3831 may have the further benefit of controlling substance abuse in patients with schizophrenia. Comorbid substance use disorder is a well-recognized obstacle to patient care. An estimated 1 out of every 3 patients with schizophrenia (33.7%) meet or have met criteria for alcohol use disorder (Regier et al, 1990). Patients with both schizophrenia and alcohol use disorder represent a common variant within the schizophrenia spectrum that is difficult to treat and is associated with an extremely poor prognosis (Dixon 1999; Koekkoek et al, 2006). Samidorphan (also referred to as ALKS 33 or RDC-0313), is structurally derived from naltrexone and is a potent μ -opioid antagonist. In clinical studies, it has been shown to block

both the subjective and physiological effects of the opioid agonist remifentanil (ALK33-004) and it is correlated with reduced drinking behavior in adults with alcohol dependence (ALK33-005). ALK3831-401 is an ongoing clinical study designed to evaluate the effect of ALKS 3831 on drinking behavior in adult subjects with schizophrenia and alcohol use disorder.

In summary, ALKS 3831 is being explored as a therapeutic agent for the treatment of schizophrenia designed to combine the antipsychotic efficacy of olanzapine with a reduced risk of weight gain and associated metabolic deficits. Development of ALKS 3831 as a fixed-dose combination of olanzapine and samidorphan has the potential to improve upon the benefit/risk profile of olanzapine alone and address a significant clinical need for patients that are currently forced to choose between treatment efficacy and safety.

5.2. Study Drugs

In this study, a fixed-dose combination of olanzapine and samidorphan will be administered in a single bilayer tablet. The following sections provide an overview of samidorphan and olanzapine. Detailed information about the study drugs can be found in the current ALKS 3831 Investigator's Brochure.

5.2.1. Samidorphan

Samidorphan is a new chemical entity in clinical development by Alkermes. It is an opioid modulator which acts primarily as an antagonist at μ opioid receptors, with mixed agonist/antagonist activity at δ and κ receptors. It is currently being investigated in combination with buprenorphine for the treatment of major depressive disorder (ALKS 5461) and in combination with olanzapine for the treatment of schizophrenia. Based on its chemical structure, samidorphan is considered a Schedule II controlled substance according to the US Drug Enforcement Agency and will require proper handling (see Section 10). At least ten clinical studies of samidorphan have been conducted to date, eight of which included subjects that received samidorphan alone (not in combination with another product). Commonly reported adverse events (AEs) observed across all studies included nausea, fatigue, and somnolence. Overall, no trends or clinically meaningful changes have been observed in clinical laboratory analytes, vital sign parameters, or electrocardiogram (ECG) data.

5.2.2. Olanzapine

Olanzapine has been available in the US since 1996 (Zyprexa[®]) and was originally approved for the treatment of schizophrenia. It has since been approved for other indications, including the treatment of schizophrenia in adolescents and bipolar disorder. The safety and tolerability profile of olanzapine is well documented, and AE labeling is supported by an extensive safety database that includes over 8,500 adult patients (Eli Lilly and Company 2017). Commonly reported AEs consistent across all or most dosage forms in short-term, placebo controlled trials include somnolence, constipation, dry mouth, accidental injury, weight gain, postural hypotension, dizziness, asthenia, fever, and abnormal gait.

5.3. Study Rationale

Phase 1 and Phase 2 studies (ALK33-301 and ALK3831-302, respectively) have demonstrated that ALKS 3831 significantly attenuates olanzapine-induced weight gain while providing similar antipsychotic efficacy for stabilization of schizophrenia symptoms. Safety and tolerability data from these studies indicate that ALKS 3831 is safe and generally well-tolerated. However, the longest treatment period assessed to date is 24 weeks. The proposed study will extend these findings and evaluate the safety and tolerability of ALKS 3831 over a 52-week period.

5.4. Dose Rationale

The selected doses of ALKS 3831 (10/10 [10 mg olanzapine/10 mg samidorphan], 15/10 [15 mg olanzapine/10 mg samidorphan], and 20/10 [20 mg olanzapine/10 mg samidorphan]) are within the approved olanzapine therapeutic dose range for the treatment of schizophrenia (Eli Lilly and Company 2017) and represent the intended commercial doses of ALKS 3831.

The 10 mg samidorphan dose was identified as the minimally effective dose based on the robust efficacy and optimal safety profile observed in a previous Phase 2 study (ALK3831-302) with that dose. A fixed dose of samidorphan was selected due to the fact that data from this study demonstrated no correlation between the ratio of samidorphan/olanzapine dose and percent change from Baseline in body weight, indicating that even with higher olanzapine doses, a fixed dose of samidorphan is sufficient to achieve maximal effect on reducing olanzapine-induced weight gain.

6. **OBJECTIVES**

6.1. **Primary Objective**

The primary objective of this study is to evaluate the long-term safety and tolerability of ALKS 3831 in subjects with schizophrenia.

7. SELECTION AND WITHDRAWAL OF SUBJECTS

7.1. Subject Inclusion Criteria

Each subject must meet all of the following inclusion criteria to be qualified to participate in this study.

- 1. Subject is willing and able to provide informed consent; subject has signed the informed consent form before initiation of any study specific procedures
- 2. Subject agrees to use an acceptable method of contraception for the duration of the study (please refer to Section 8.4.1 for additional details regarding contraception)
- 3. Subject is willing and able to follow the study procedures as outlined in the protocol
- 4. Subject has the potential to benefit from the administration of ALKS 3831, in the opinion of the Investigator
- 5. Subject has completed the 4-week Treatment Period (all visits up to and including Visit 6, End of Treatment) in the antecedent study, ALK3831-A305, within 7 days

7.2. Subject Exclusion Criteria

Each subject must not have any of the following conditions to be qualified to participate in this study.

- 1. Subject has any finding that, in the view of the Investigator or Medical Monitor, would compromise the safety of the subject or affect their ability to fulfill the protocol visit schedule or visit requirement
- 2. Subject is currently taking medications that are contraindicated with olanzapine use or exhibit drug-interaction potential with olanzapine will be defined and prohibited at the discretion of the Principal Investigator (PI)
- 3. Subject has a positive test for drugs of abuse at study entry
- 4. Subject is pregnant, planning to become pregnant, or breastfeeding during the study

7.3. Subject Withdrawal

A subject may be discontinued from the study at any time if the subject, Investigator, or the Sponsor determines that it is not in the best interest of the subject to continue participation. If a subject has an absolute neutrophil count (ANC) $< 1.0 \times 10^3$ per µL or HbA1c $\geq 6.5\%$ at any time during this extension study, the subject will be discontinued from the study. Other reasons for discontinuation include the following:

- AEs
- Lack of Efficacy
- Lost to follow-up
- Withdrawal by subject

- Protocol Deviation (noncompliance with study drug or study procedures)
- Pregnancy
- Study terminated by Sponsor
- Other

If a subject withdraws from the study for any reason, any ongoing AEs will be followed until resolution, until deemed stable by the Investigator, or until the subject is deemed by the Investigator to be lost to follow-up. If, in the opinion of the Investigator, it is necessary to monitor a subject beyond the Safety Follow-up Visit, the Follow-up Period may be extended, as necessary. In such instances, the Sponsor and the Investigator will agree to an acceptable follow-up schedule.

In the event that a subject chooses to withdraw from the study, the Investigator should make a reasonable effort to ascertain the reason(s) for withdrawal, while fully respecting the subject's rights. Enrolled subjects are to be asked to return to the clinic for an Early Termination (ET) Visit and to complete a subsequent Safety Follow-up Period. The ET Visit should be scheduled as close as possible to the subject's last dose and will mimic the assessments scheduled to be conducted at the End of Treatment (EOT) Visit (Visit 28, Table 3). If the subject fails or refuses to return to the study center, an attempt must be made to contact the subject by telephone in order to assess as many safety and efficacy parameters as possible. All data collected over the telephone must be documented and kept in the subject's record.

The Investigator must maintain a record of all subjects who fail to complete the study. The reason for study discontinuation will be documented and entered on the appropriate electronic case report form (eCRF). If a subject is lost to follow-up, a reasonable attempt to contact the subject must be made and documented.

7.4. Replacement of Subjects

Subjects prematurely discontinued from the study will not be replaced.

8. STUDY DESIGN

8.1. Overall Study Design and Plan

Subjects that have completed the 4-week Treatment Period of the antecedent study, ALK3831-A305, within the past 7 days are eligible to be enrolled in the study. Subjects completing the 4-week Treatment Period of the antecedent study, ALK3831-A305, as inpatients may continue as inpatients for up to 1 week in this extension study. These subjects may be discharged from the inpatient unit at any time during this week based on Investigator's judgment.

Subjects enrolled in the study will be started on ALKS 3831 10/10 (10 mg olanzapine/10 mg samidorphan). The ALKS 3831 dose may be increased to 15/10 (15 mg olanzapine/10 mg samidorphan) or 20/10 (20 mg olanzapine/10 mg samidorphan) during the first week of treatment or thereafter, based on Investigator discretion. For subjects entering this study as outpatients, study staff will check in with them by phone on Day 3 to assess tolerability and determine if a dose increase to ALKS 3831 15/10 or 20/10 is needed. An Unscheduled Visit will be arranged mid-Week 1 for subjects requiring a dose increase. Following a dose increase, the dose may be decreased back to 15/10 or 10/10 if there are tolerability issues. Thus, dosing is flexible and subjects will receive ALKS 3831 10/10, 15/10, or 20/10 throughout the duration of the study, based on Investigator discretion. Dose adjustments can only be performed on-site at the study center. Subjects requiring dose adjustments between scheduled visits should arrange an Unscheduled Visit for the following procedures: study drug return, adherence review, and study drug dispensation.

Safety assessments will include AE monitoring, clinical laboratory testing, vital signs, weight and waist circumference assessments, 12-lead ECGs, movement disorder assessments, including the Abnormal Involuntary Movement Scale (AIMS), Barnes Akathisia Rating Scale (BARS), and Simpson Angus Scale (SAS), and the Columbia-Suicide Severity Rating Scale (C-SSRS).

[figure not shown]
Efficacy assessments to evaluate the durability of treatment effect will include Positive and Negative Syndrome Scale (PANSS) and Clinical Global Impressions-Severity (CGI-S).

Additional assessments include Impact of Weight on Quality of Life–Lite Questionnaire (IWQOL-Lite), Cigarette Use, and EuroQOL-5D (EQ-5D).

Subjects completing 52 weeks of treatment with study drug will be eligible to continue in the open-label, long-term safety study (ALK3831-A308) and will continue to receive ALKS 3831. Subjects not continuing in the ALK3831-A308 long-term safety study will enter a 4-week Safety Follow-up Period. The overall schedule of visits and assessments for each Treatment Group is provided in Table 3.

A schematic of the study design is provided in Figure 1.

Figure 1: Study Design Schematic

*Visits will occur weekly for the first 2 weeks, then biweekly thereafter. Outpatient subjects will be contacted by phone on Day 3 to determine if a dose increase is needed, and, if so, an unscheduled visit will be arranged mid-Week 1. The dose may be adjusted to either 10/10, 15/10, or 20/10 mg throughout the study period, based on Investigator discretion, and such dose adjustments will require subjects to visit the study site

8.2. Schedule of Visits and Assessments

The schedule of assessments is shown in Table 3.

A visit window of ± 2 days is permitted throughout the Treatment Period and the Follow-up Period (Visits 2-30). For a missed visit, the site should attempt to contact the subject to reschedule.

Premature discontinuation procedures are provided in Section 7.3.

On Day 3, study staff will check in with outpatient subjects by phone to determine if a dose increase to ALKS 3831 15/10 or 20/10 is needed. If, in the opinion of the Investigator, a dose increase is warranted, an Unscheduled Visit will be arranged mid-Week 1. The following procedures will be performed during the Unscheduled Visit: study drug return, adherence review, and study drug dispensation.

Dose adjustments can only occur on-site and require subjects to come to the study center. Throughout the study, subjects requiring dose adjustments between scheduled visits may arrange an Unscheduled Visit (same procedures as mid-Week 1 Unscheduled Visit described above).

Table 3:Schedule of Assessments

												0	pen I	abel	Trea	tmen	t Peri	iod											u	low- 1p riod
Visit ^a	1 ^b	2 [°]	3	4	5	6	7	8	9	10	11	12	13	14	15	16	17	18	19	20	21	22	23	24	25	26	27	28/ ET/ EOT	29 ^d	30
Study week	-	1	2	4	6	8	10	12	14	16	18	20	22	24	26	28	30	32	34	36	38	40	42	44	46	48	50	52	54	56
Informed Consent	х																													
Eligibility Criteria	x																													
Pregnancy Testing ^e	х							Х						Х						Х										
Urine Drug Screen	Х																													
Weight		Х	Х	Х	Х	Х		Х		Х		Х		Х		Х		Х		Х		Х		Х		Х		Х		Х
Waist Circum- ference		Х	х	х	х	Х		Х		Х		Х		Х		Х		Х		Х		Х		Х		Х		Х		X
Vital Signs ^g		Х	Х	Х	Х	X		Х		Х		Х		Х		Х		X		Х		Х		Х		Х		Х		Х
Laboratory Samples ^h				Х				Х						Х						Х								Х		
ECG				Х				Х						Х						Х								Х		
Physical Exam				X				Х						Х						Х								Х		
PANSS ⁱ				Х		Х		Х						Х						Х								Х		
CGI-S				Х		Х		Х		Х		Х		Х		Х		Х		Х		Х		Х		Х		Х		
AE ^j		Х	Х	Х	Х	Х	Х	Х	Х	Х	Х	Х	Х	Х	Х	Х	Х	Х	Х	Х	Х	Х	Х	Х	Х	Х	Х	Х	Х	Х
ConMed ^j		Х	Х	Х	Х	Х	Х	Х	Х	Х	Х	Х	Х	Х	Х	Х	Х	Х	Х	Х	Х	Х	Х	Х	Х	Х	Х	Х	Х	Х
C-SSRS ^k		Х	Х	Х	Х	Х	Х	Х	Х	Х	Х	Х	Х	Х	Х	Х	Х	Х	Х	Х	Х	Х	Х	Х	Х	Х	Х	Х	Х	Х

Table 3:Schedule of Assessments (Continued)

												Ор	en La	abel T	reati	ment	Perio	d											Foll u Per	р
Visit ^a	1 ^b	2°	3	4	5	6	7	8	9	10	11	12	13	14	15	16	17	18	19	20	21	22	23	24	25	26	27	28/ ET/ EOT	29 ^d	30
Study week	-	1	2	4	6	8	10	12	14	16	18	20	22	24	26	28	30	32	34	36	38	40	42	44	46	48	50	52	54	56
Abnormal Movement Scales				x				х						X						X								Х		
IWQOL	Х			Х				Х						Х						Х								Х		
EQ-5D	Х			Х				Х						Х						Х								Х		
Cigarette Use	Х			X				Х						х						х								Х		
Emergency Treatment Card ^m	X	Х	х	х	x	х	Х	X	Х	X	X	X	Х	Х	Х	Х	Х	Х	Х	Х	Х	Х	Х	Х	X	Х	X	Х		
Study Drug Dispensation	Х	Х	Х	Х	X	Х	Х	Х	Х	Х	х	х	Х	х	Х	х	Х	х	х	х	х	Х	х	х	х	х	х			
Study Drug Adherence Review ⁿ		Х	х	x	x	х	Х	х	Х	х	x	х	Х	х	X	X	X	X	X	X	X	Х	X	х	X	X	X	Х		

Abbreviations: AE=adverse event; CGI-S=Clinical Global Impression-Severity; ConMed=concomitant medication; C-SSRS=Columbia-Suicide Severity Rating Scale; ECG=electrocardiogram; EOT=End of Treatment; EQ-5D=EuroQOL-5D; IWQOL=Impact of Weight on Quality of Life; PANSS=Positive and Negative Syndrome Scale

^a A visit window of ±2 days is permitted throughout the Treatment Period and the Follow-up Period (Visits 2-30)

^b Visit 1 must occur within 7 days of the EOT Visit (Visit 6) of the antecedent study, ALK3831-A305, and may occur on the same day. Assessments from ALK3831-A305 Visit 6 will constitute the Baseline/Screening assessments for this extension study

^c On Day 3, study staff will contact outpatient subjects by phone to determine if a dose increase to ALKS 3831 15/10 or 20/10 is needed. An Unscheduled Interim Visit will be arranged for subjects requiring a dose adjustment for study drug return and adherence review and study drug dispensation. Any subsequent dose adjustments throughout the study require subjects to come to the site for either a scheduled or unscheduled visit

^d Follow-up Visits (Visits 29 and 30) are not required for subjects who enroll in ALK3831-A308

^e Urine pregnancy test prior to dosing at Visit 1 and at all subsequent specified visits

Protocol ALK3831-A306 v 3.0 (Amendment 2.0)

- ^f Urine drug screen via dipstick prior to dosing on Day 1 for subjects who did not receive a urine drug screen at Visit 6 of the ALK3831-A305 study, or for subjects for whom Visit 1 of this study is not the same day as Visit 6 of the ALK3831-A305 study. Urine drug screen includes opiates, phencyclidine (PCP), amphetamine/methamphetamine, and cocaine
- ^g Vital signs include orthostatic blood pressure and heart rate, respiratory rate, and oral body temperature. Blood pressure, pulse rate, and respiratory rate will be taken after the subject has been supine for 5 minutes and once again after the subject has stood for 2 minutes
- ^h Subjects must fast (no food or drink except water) for at least 8 hours before laboratory draws. Laboratory draws are to be conducted in the morning for all specified visits
- ⁱ PANSS should be administered before other psychiatric assessments at each specified study visit
- ^j AEs ongoing at the end of the antecedent study or concomitant medications continuing from the antecedent study will be carried over and followed through until resolution
- ^k The "Since Last Visit" version to be used at all visits
- ¹ Abnormal movement scales include the following: Abnormal Involuntary Movement Scale (AIMS), Barnes Akathisia Rating Scale (BARS), and Simpson-Angus Scale (SAS)
- ^m Emergency treatment card to be dispensed at Visit 1, confirmed at subsequent timepoints, and collected at Visit 28, EOT
- ⁿ Calls should be made in weeks between in-person study visits to ensure subjects are continuing to stay adherent with medication. An Unscheduled Visit will be arranged for any dose adjustments required between planned visits when subjects will come to the site for study drug return and new drug dispensation

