8.3.12. Emergency Treatment Card

An emergency treatment card will be distributed to each subject and collected from each subject at the timepoints indicated in Table 3. The card will indicate that the subject is receiving an opioid antagonist and olanzapine, and will include the PI's contact information, a suggested pain management plan and information regarding opiate blockade. Subjects will be instructed to keep the card with them at all times. Study personnel will confirm that subjects have the card in their possession at each study visit, as indicated in Table 3.

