8.4.4. Pain Management

Because ALKS 3831 contains samidorphan, a μ -opioid receptor antagonist, patients may experience reduced or ineffective analgesia when taking an opioid analgesic agent concurrently with ALKS 3831, including several days after last dosing of ALKS 3831.

In the event of an emergency, pain management of the subject should include the following:

- Regional analgesia or use of non-opioid analgesics
- If opiate anesthesia or analgesia is required, the subject should be continuously monitored, in an anesthesia care setting, by persons not involved in the conduct of the surgical or diagnostic procedure. The opioid therapy must be provided by individuals specifically trained in the use of anesthetic drugs and the management of the respiratory effects of potent opioids, specifically the establishment and the maintenance of a patent airway and assisted ventilation
- Close monitoring by appropriately trained personnel in a setting equipped and staffed for cardiopulmonary resuscitation

For subjects requiring emergency opioid analgesics prior to dosing, the study drug should not be administered. If opioid analgesics are required after the study drug has been dosed, it may take several days for opiate sensitivity to be restored, since samidorphan is an opioid antagonist and could interfere with opioid-mediated pain management.

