9. TREATMENT OF SUBJECTS

9.1. Study Drug Dose and Administration

Study drugs include:

• ALKS 3831 10/10 (10 mg olanzapine/10 mg samidorphan), 15/10 (15 mg olanzapine/10 mg samidorphan), or 20/10 (20 mg olanzapine/10 mg samidorphan) administered as a coated bilayer tablet

At Visit 1 and all subsequent visits until EOT, subjects will be given blister cards containing study drug to take at home. Subjects will be instructed to take one tablet by mouth each day, preferably at bedtime. Dosing may be switched to another time, at the Investigator's discretion, if there are tolerability problems; however, frequent switching is discouraged.

Subjects will be instructed to keep all unused tablets in their blister card and to return unused tablets to the study site at their next visit. If dosing is to occur at that visit, the dose should be taken from the subject's next blister card, not from the card they are returning.

If a dose is missed or forgotten, subjects will be instructed to resume regular dosing the following night. Subjects will be instructed not to take a double dose to try to "make up" for the missed dose.

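### The emergency treatment card is collected at Visit 28/EOT, often within about a day of the last dose, although the protocol warns that opioid analgesia may be impaired for several days after dosing stops

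*Protocol*

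**What the plan says.** Protocol section 8.2, Table 3, footnote m sets the life of the card: "Emergency treatment card to be dispensed at Visit 1, confirmed at subsequent timepoints, and collected at Visit 28, EOT". The card row is marked from Visit 1 through the shared 28/ET/EOT column and is empty at Visits 29 and 30. Section 8.3.12 refers to Table 3 for the timing of collection. It describes the content as follows: "The card will indicate that the subject is receiving an opioid antagonist and olanzapine", together with the principal investigator's contact details, a suggested pain plan and information on opiate blockade. Subjects are to carry it at all times.

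Section 8.4.4 says that opioid analgesia may be reduced or ineffective while on drug, "including several days after last dosing of ALKS 3831". It adds that if opioids are needed after a dose, "it may take several days for opiate sensitivity to be restored".

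On dosing, section 9.1 says: "Subjects will be instructed to take one tablet by mouth each day, preferably at bedtime". On early termination, section 7.3 says that the ET Visit "will mimic the assessments scheduled to be conducted at the End of Treatment (EOT) Visit" and should be held as close as possible to the last dose. It also asks these subjects "to complete a subsequent Safety Follow-up Period".

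**The concern.** The card exists so that emergency staff outside the trial learn that the patient has an opioid antagonist on board and how pain should be managed. Section 8.4.4 says that this need may outlast dosing by several days, yet Table 3 takes the card away at the visit that ends treatment. Nothing in the protocol lets the subject keep it or provides a replacement.

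Those exposed are completers who do not continue into ALK3831-A308 and early terminators who attend an ET Visit soon after their last dose. If one of them needs emergency analgesia in those days, staff who do not know about the antagonist have no reason to apply the precautions in section 8.4.4: regional or non-opioid analgesia where possible and, if opioids are required, continuous monitoring in an anesthesia care setting.

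**Working it through.** The plan states no figure to reproduce. The check compares the visit schedule with the warning in section 8.4.4.

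**Inputs**
- Collection: Visit 28 (week 52), from Table 3 and footnote m.
- Next visit: Visit 29 (week 54), required only for subjects not entering A308 (Table 3, footnote d).
- Visit window: ±2 days on Visits 2 to 30 (footnote a).
- Dosing: once daily, preferably at bedtime (9.1). No drug is dispensed at Visit 28 (Table 3).
- Supply: biweekly blister cards hold 16 tablets for 14 days (10.2), so dosing can run up to Visit 28 even at +2 days.
- Laboratory samples are due at Visit 28 and are drawn in the morning (Table 3, footnote h).
- Period of possible blockade after the last dose: several days, with no number given (8.4.4). **Assumption:** D = 3 to 7 days.

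**Last dose to collection.** For an adherent bedtime doser, Visit 28 follows the last dose by about half a day to one day. Section 9.1 allows another dosing time, so a same-day dose remains possible. Take d = 0 to 1 day.

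**Days of the flagged period left when the card is collected** = max(0, D − d)

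| Subject | d (days) | Lower (D = 3) | Upper (D = 7) |
|---|---|---|---|
| Completer at EOT | 0 to 1 | 3 − 1 = 2 | 7 − 0 = 7 |
| ET attended | 1 | 3 − 1 = 2 | 7 − 1 = 6 |
| ET attended | 3 | 3 − 3 = 0 | 7 − 3 = 4 |
| ET attended | 7 or more | 0 | 0 |

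For the typical bedtime completer (d = 0.5 to 1) the range is 3 − 1 = 2 to 7 − 0.5 = 6.5 days.

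**Would collection at Visit 29 close the gap?** Week 54 − week 52 = 14 days. With ±2 days on each visit, the interval is 14 − 4 = 10 to 14 + 4 = 18 days. The minimum of 10 exceeds the assumed maximum of 7, so for completers it does at every window combination.

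**Time the card is held beyond the flagged period.** Nominally, Visit 29 falls 14 to 15 days after the last dose, so the excess is 14 − 7 = 7 to 15 − 3 = 12 days. With visit windows it is 10 + 0 − 7 = 3 to 18 + 1 − 3 = 16 days.

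**The case against.** The strongest counter-argument is that collection at the end of dosing has a logic: the card says the subject is receiving an opioid antagonist, and that stops being true. Leaving it with an off-drug subject for two more weeks could mislead staff in the other direction, and subjects who miss Visit 29 would keep it. This is a real cost. It is a reason to put the last-dose date on the card, but it does not remove the gap. The date helps only partly, because the documents do not say how long blockade lasts.

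The size of the gap is also assumed. Section 8.4.4 says only that the effect may occur and may take several days to pass, so every figure for remaining days depends on the 3-to-7-day range. That stands. What does not depend on it is that about one day is shorter than several days.

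The early-terminator part is weaker. Footnote m names only Visit 28/EOT, and section 7.3 speaks of assessments, which need not include taking back a card. The shared column makes collection at ET the likelier reading, but it is an inference. Subjects who never attend ET keep the card, and a late ET shortens or closes the gap. Nor do the documents give an interval from ET to Visit 29, so the 10-to-18-day result carries over to this group only if they follow the same follow-up spacing.

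Finally, the consent pages are not available, so other warnings to subjects cannot be excluded. Section 8.4.2 also advises avoiding opioid agonists during the study period. Neither would necessarily reach outside emergency staff, for whom the card is meant.

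**Conclusion.** The concern holds. As written, the schedule withdraws the card inside a period that the protocol identifies as possibly at risk. For completers entering Safety Follow-up this follows directly from footnote m, Table 3 and the dosing schedule. About 2 to 7 days of the period remain if several days means 3 to 7. For early terminators it is a likely reading, with 2 to 6 days remaining at an ET Visit one day after the last dose and none at seven days or later.

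The documents give neither the number of subjects who will decline A308 nor the rate of emergencies requiring opioids, so no count is claimed. Subjects who enter A308 stay on drug and are outside this point; these documents do not say whether that study issues its own card. No endpoint, population or analysis changes. This is a patient-safety inconsistency that should be corrected because the correction costs little.

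**What to change.** For subjects not entering ALK3831-A308, amend footnote m and the Table 3 card row so that the card is confirmed at Visit 28/ET and collected at Visit 29. At Visit 28 or ET, write the date of the last dose on the card, so that its present-tense statement about the antagonist can be read correctly later. The amended footnote should name ET explicitly and state when Visit 29 falls after an ET Visit.

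The cost is one table row, one footnote and one entry on the card. No visit is added: Visit 29 already exists for these completers, and section 7.3 already asks early terminators to complete follow-up. The drawbacks are some unreturned cards and a card held nominally 7 to 12 days longer than the assumed period requires.
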